There has been no research on the value of cyanoacrylate embolization in the treatment of patients with chronic venous insufficiency and ulceration. Venous leg ulceration costs the NHS £600 million per year and affect 1.7% of the elderly population^{4,5}, making it a significant health problem that justifies further study.

We propose to define whether cyanoacrylate embolization is a safe and effective method of occluding incompetent lower limb veins in patients with venous ulceration of the lower limb.

PRIMARY OBJECTIVES

Our primary objectives are to answer the following research questions:

1. Does VenaSeal[™] cyanoacrylate occlusion of incompetent lower limb veins increase the rate of healing and shorten healing time in patients with an ipsilateral venous ulcer?

2. What is the incidence of venous recanalization following VenaSeal[™] cyanoacrylate occlusion for the treatment of ipsilateral venous leg ulcer?

3. Does VenaSeal[™] cyanoacrylate occlusion of incompetent lower limb veins improve quality of life and symptom severity scores in patients with venous leg ulcer?

4. What is the adverse effect profile of VenaSeal[™] cyanoacrylate occlusion of incompetent lower limb veins for the treatment of venous leg ulcers?

The overall aim of the research is to determine whether VenaSealTM cyanoacrylate occlusion of incompetent lower limb veins is an effective, safe and acceptable treatment in patients with ipsilateral venous leg ulcer.

STUDY DESIGN

This study is a randomised controlled trial comparing VenaSeal[™] cyanoacrylate occlusion plus normal treatment with normal treatment alone in patients with ipsilateral venous leg ulceration and Duplex-detected lower limb vein incompetence.

Normal treatment in both groups is defined as nurse-led dressing of the ulcer using a low adherence dressing and four-layer compression bandaging. Patients randomized to the treatment arm will also undergo cyanoacrylate occlusion using the VenaSealTM system.

The study will begin with 5 patients undergoing VenaSeal treatment as 'roll in' cases. Following these patients' treatment, the study proper will begin. Randomisation software will be used to allocate patients who fulfil inclusion / exclusion criteria to either the treatment arm or the non-treatment arm. This will be done to a 1:1 ratio, with 25 patients in each arm.

Patients will be followed up via face-to-face consultations at 3, 6 and 12 months post-randomisation.

INCLUSION CRITERIA

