- 1. Venous ulcer of the lower limb at least 2cm² (CEAP classification C6)
- 2. Ulceration present for >6 weeks and <6months despite treatment.
- 3. Ipsilateral lower limb vein incompetence of >0.5 seconds duration, confirmed by venous duplex imaging.
- 4. Aged ≥18 years.
- 5. Willing and able to provide informed consent.
- 6. Ipsilateral ankle-brachial pressure index ≥ 0.8 at the time of randomisation.

EXCLUSION CRITERIA

- Non-venous cause of ulceration: peripheral arterial disease (ABPI < 0.8), vasculitis, neuropathy, recent lower limb trauma, chronic dermatitis, pyoderma gangrenosum, malignancy, chronic osteomyelitis or any other lower limb pathology that may be contributing to the ulceration, in the opinion of the investigator.
- 2. Inability to tolerate or comply with lower limb compression therapy
- 3. Inability to receive prompt endovenous treatment
- 4. Unwilling or unable to provide informed consent.
- 5. Current enrolment in another study pertaining to venous ulceration.
- 6. Primary or secondary immunosuppression.
- 7. Previous treatment of the target vein or other venous surgery that may compromise the study, in the opinion of the research team.
- 8. Patient has pre-planned surgical intervention or endovascular procedure scheduled up to 30 days after the index procedure.
- 9. Currently pregnant.
- 10. Duplex evidence of deep venous incompetence or occlusion.
- 11. Clinical evidence of post-thrombotic syndrome.
- 12. Incompetent vein considered too tortuous to allow VenaSealTM treatment.
- 13. Inability to tolerate VenaSeal[™] treatment.

PRIMARY ENDPOINTS

The primary outcome measure is the rate of healing in leg ulcer surface area. The margins of the ulcer will be traced onto an acetate sheet and measured using a planimeter¹. From these weekly measurements (every 7 days +/- 2 days), it will be possible to calculate the

¹ The ulcer margins are traced onto a sheet of acetate. The acetate is then placed on a flat surface, and a planimeter is used to measure the surface area within the outlined margins. The planimeter is calibrated prior to use to ensure accuracy. For this study, a Planix 7 (Tamaya Technics, Tokyo, Japan) will be used.

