rate at which the ulcer is healing. The time to healing (defined as complete overgrowth of the epithelial surface in the opinion of the researcher) will also be recorded. All measurements will be taken in duplicate by two members of the research team. The point at which the ulcer has healed represents the patient reaching the primary endpoint. Once healing has occurred, the patient will not be required to return to the clinic for weekly assessments, but will be asked to complete the questionnaires that measure the secondary endpoints at 3, 6 and 12 months (as described below), until the one year follow up period is complete.

Measuring rate of healing is important as it allows legitimate comparison between patients with differently sized ulcers. Time to healing is extremely important, as healing reduces the burden of symptoms and the impact on quality of life, and is the primary target for all patients and clinicians managing venous leg ulcer. Ulcer recurrence will not be assessed, as the follow up period is limited to 12 months.

PATIENT SAFETY

All patients will be treated in line with local and National Health Service (NHS) health and safety policies. All VenaSealTM treatments will adhere to the Instructions For Use (IFU) supplied with the product. All patients will have immediate access to acute medical and surgical services provided by the University Hospital of South Manchester NHS Foundation Trust in the event of adverse effects or complications of treatment.

PROCEDURE / INTERVENTION DESCRIPTION

All patients will be randomised to receive standard venous leg ulcer management, or standard venous leg ulcer management plus VenaSeal occlusion of incompetent lower limb veins.

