Once the desired length of vein has been treated, the device will be withdrawn and the wound compressed manually until haemostasis has been achieved. A small dressing will be placed at the puncture site, followed by dressing of the venous ulcer with a low adherence dressing and four-layer compression bandaging applied by a specialist leg ulcer clinic nurse, aiming for a pressure of 40mmHg at the ankle and graduated towards the knee. Written advice will be provided to emphasise the need for patients to elevate their lower limb whenever possible, along with additional advice on how to manage the compression bandages. Patients will return to the leg ulcer clinic weekly to continue the usual leg ulcer treatment of wound care, dressings and compression bandaging.

Patients randomised to the non-treatment arm will receive the usual treatment for venous leg ulcer, specifically routine wound care, dressings, and the application of four-layer compression bandaging applied by a specialist leg ulcer clinic nurse, aiming for a pressure of 40mmHg at the ankle. The same written advice will be provided to this group. All compression bandages for patients in both arms will be applied by nursing staff who work in the specialist leg ulcer service.

If any participant requires further vascular surgical intervention, including treatment of perforators (e.g. treatment with ClosureFast[™] RFS Stylet), then this will be arranged and offered as for any other non-research participant. The requirement for further interventions directly related to the patient's venous disease will be recorded by the research team, if it occurs within the 12 month follow up period.

SECONDARY ENDPOINTS

The secondary measures will be measured at baseline, 3, 6 and 12 months and are as follows:

1. The validated EQ-5D, SF-36 and VEINES-QoL scores^{6,7} will be used to assess quality of life, self-assessment of health, and severity of symptoms in both groups. Venous leg ulcer is associated with reduced quality of life and prolonged, often severe symptoms, so this is an important assessment.

2. The rate of venous recanalization seen on duplex ultrasound is also important, to ensure that the venous occlusion has persisted.

3. Patient satisfaction scores

4. Adverse event recording will also take place, which is an important step in defining the safety of the procedure for this purpose. These will be described in the final report and in any other presentations of the work.

5. Health economic analysis:

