
- a) Cost and frequency of visits to wound care and outpatient clinic.
- b) District nurse visit costs
- c) Inpatient treatment costs

d) Costs of complications of the treatment, or of non-healing ulcers (for example, acute or chronic infections).

STATISTICAL METHOD / RATIONALE

The main aim of the pilot study is to inform a larger, more definitive study by assessing feasibility and describing the main outcomes for the patients in the study. As such, the main analysis will be summary statistics. Simple statistical tests will be used to compare the groups, though these analyses are exploratory and non-definitive since the study is a pilot and has a limited sample size.

Time from intervention to healing, one part of the primary outcome, will be described in the two randomised groups using medians, interquartile ranges and ranges (minimum to maximum), assuming the data will be non-normally distributed. The other component of the primary outcome, the mean % ulcer healed per week², will be calculated for each patient

² The mean % ulcer healed per week will be calculated up to the point where the ulcer has fully healed (the primary endpoint). No further measurements will be calculated after this point.

and summarised in the two groups using means, standard deviations and ranges, assuming the data will be normally distributed.

The secondary endpoints will also be assessed using descriptive statistics. The composite VEINES-QOL/Sym score will be calculated using the intrinsic scoring method detailed in the Bland et al. validation paper.⁷ The composite summary scores will be described at each point they are assessed using means, standard deviations and ranges.

The rate of venous recanalization in each group will be summarised using frequencies and percentages. The number of adverse events and percentage in each group will be presented.

The statistical analyses used to compare the groups will be independent samples t-tests, Mann-Whitney U tests, and chi-squared tests.

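### Healing time is counted from an intervention that control patients never receive, so the two arms have no common start date and the VenaSeal arm can look faster with no treatment effect

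*Protocol*

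**What the plan says.** Statistical Method / Rationale fixes the start of the clock: "Time from intervention to healing, one part of the primary outcome". The same sentence applies this to both randomised arms. The summaries are medians, interquartile ranges and ranges, and the Mann-Whitney U test is among the listed comparisons.

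Primary Endpoints defines the end of the interval but not its start: "The time to healing (defined as complete overgrowth of the epithelial surface in the opinion of the researcher) will also be recorded".

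Procedure / Intervention Description gives controls no procedure: "Patients randomised to the non-treatment arm will receive the usual treatment for venous leg ulcer", meaning wound care, dressings and four-layer compression.

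Study Design dates the scheduled visits differently: "Patients will be followed up via face-to-face consultations at 3, 6 and 12 months post-randomisation".

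The only text on how soon the procedure follows allocation is an exclusion criterion: "Inability to receive prompt endovenous treatment". No interval in days or weeks is given.

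**The concern.** A randomised comparison of times needs a start date that exists for every patient and means the same in both arms. A procedure date exists in one arm only. Whoever prepares the data must choose a date for controls, and the Protocol does not say which. Randomisation is the obvious choice, because it is the only dated origin the Protocol uses for follow-up.

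With that choice the arms are measured differently. Time between randomisation and procedure counts as healing time for controls and is discarded for VenaSeal patients. Those who heal during the wait have no positive time from intervention and would probably be dropped. Ulcers are traced weekly, so a wait of one week is already a full measurement interval.

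At stake is one of the two components of the primary outcome, and the medians that a larger trial would be planned on.

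**Working it through.** The Protocol has no power calculation, assumed median, spread or significance level, so there is no figure of its own to reproduce. The check asks what different start dates do when the treatment has no effect.

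**From the Protocol:** 25 patients per arm, 12 months of follow-up, Mann-Whitney U test.

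**Assumed:** controls timed from randomisation; wait d of 0, 1, 2 or 4 weeks; median healing time m of 12 or 24 weeks from randomisation, identical in both arms; two-sided 5% level; six shapes of healing-time distribution.

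**Closed form.** Let T be time from randomisation to healing, with survival function S. The VenaSeal arm is recorded as T − d among patients with T > d. Its median M solves S(d + M) = 0.5 × S(d). For a Weibull distribution with shape k and median m, this gives

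M = (m^k + d^k)^(1/k) − d.

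- k = 1 (constant hazard): M = m + d − d = m, so there is no shift at any wait.
- k = 2 (rising hazard), m = 12, d = 1: √145 − 1 = 11.04, a shift of 0.96 weeks.
- k = 2, m = 12, d = 2: √148 − 2 = 10.17, a shift of 1.83 weeks.
- k = 2, m = 12, d = 4: √160 − 4 = 8.65, a shift of 3.35 weeks.

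The share of VenaSeal patients healed before the procedure is 1 − 2^(−(d/m)^k). With k = 1, m = 12 and d = 4 it is 1 − 2^(−1/3) = 20.6%, about 5 of 25. With k = 2 it is 1 − 2^(−1/9) = 7.4%.

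**Simulation.** 4,000 null trials per scenario. VenaSeal patients healed before the procedure were dropped, and follow-up was cut at 52 weeks from randomisation. Each cell gives the false median advantage of the VenaSeal arm in weeks, then the Mann-Whitney rejection rate; ranges cover m = 12 and m = 24.

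| Healing pattern | d = 1 | d = 2 | d = 4 |
|---|---|---|---|
| Weibull k = 1 | none; 5.1-6.6% | none; 4.4-6.0% | none; 5.0-6.5% |
| Weibull k = 1.5 | 0.8-0.9; 5.3-6.4% | 1.5-1.7; 6.3-9.1% | 2.5-2.9; 10.0-15.9% |
| Weibull k = 2 | 1.0; 5.8-6.8% | 1.8-1.9; 7.8-16.1% | 3.4-3.7; 15.6-39.3% |
| Lognormal σ = 0.5 | 1.0; 6.1-9.6% | 2.0; 9.8-22.9% | 3.9-4.0; 22.3-62.7% |
| Lognormal σ = 0.8 | 1.0; 6.4-6.9% | 1.8-2.0; 9.1-11.8% | 3.0-3.7; 15.5-20.2% |
| Lognormal σ = 1.2 | 0.6-0.9; 5.6-8.0% | 0.7-1.3; 6.3-10.1% | 0.2-1.4; 5.7-11.1% |

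The simulation error of a 5% rate is √(0.05 × 0.95 / 4000) = 0.34 percentage points, so 4.4% is not distinguishable from 5%. The slight excess for k = 1 arises at m = 24, where the VenaSeal arm has less follow-up left after the procedure.

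**After the fix.** Timing both arms from randomisation is the d = 0 case. The median difference is then at most 0.2 weeks and the rejection rate is 4-6% in every scenario.

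**The case against.** The strongest reply is that the word intervention may cover either allocated management. The sentence on allocation stands under the heading Procedure / Intervention Description: "All patients will be randomised to receive standard venous leg ulcer management, or standard venous leg ulcer management plus VenaSeal occlusion". Read that way, both arms have a start. This is possible, but it does not settle the matter. Elsewhere in the body text the word refers to surgical or theatre procedures. Inclusion criterion 2 requires an ulcer that has persisted despite treatment, so usual care began before randomisation and gives controls no clear date. Even on this reading the two starts need not coincide.

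The second reply concerns size, and much of it stands. A reader might infer that the treated clock certainly starts later and that VenaSeal will certainly look faster. The Protocol does not support that. It does not say how controls are timed, it states no wait, and the exclusion for patients who cannot be treated promptly weighs against the longer waits. With a constant hazard the medians do not move. By the formula above, a hazard that falls from the start (k < 1) would even move them the other way. The largest false-positive rates need a narrow distribution, a 12-week median and a 4-week wait together.

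Third, the Protocol makes summary statistics the main analysis and calls its tests exploratory. That lowers the severity. It does not remove the defect, because the medians themselves are affected and the stated aim is to inform a definitive study.

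Two further inferences should be resisted. Exclusion criterion 8, with its window "scheduled up to 30 days after the index procedure", also refers to a procedure that controls lack, but it screens eligibility and sets no outcome clock. Nor is all other follow-up dated from randomisation: the weekly tracings have no stated origin.

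**Conclusion.** The defect is real. The Protocol states a start date for a primary outcome component that cannot be applied alike to the two randomised arms. This is a rule fixed badly, not a detail left to a statistical analysis plan.

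The resulting bias is possible, not established. It requires controls timed from randomisation, a material wait before the procedure, and a healing hazard that is not constant. Where these hold, in the scenarios run, it favours VenaSeal by up to about the length of the wait. Over all those scenarios the false median advantage is 0 to about 1 week at a 1-week wait, 0 to 2 weeks at 2 weeks, and 0 to 4 weeks at 4 weeks. Even where the medians do not shift, some VenaSeal patients have no defined time: with a constant hazard, about 3-6% at a 1-week wait and 11-21% at 4 weeks. Waits, medians, distributions and the 5% level are all assumptions. The wording should be corrected before analysis, although the exploratory status of the comparison limits the harm.

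**What to change.** In Statistical Method / Rationale, define the component as time from randomisation to healing, in both arms. Include all randomised patients in the arm to which they were allocated. That is straightforward with this origin, since a patient who heals before the procedure, or never has it, still has a valid start date. Report the interval from randomisation to procedure descriptively in the VenaSeal arm, so that readers can see how much waiting the result contains. No limit on that wait is proposed here.

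The cost is a one-line change of wording and the recording of one date. The VenaSeal result may look slightly less favourable, because time spent waiting then counts in that arm as well.

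### Time to healing is given complete-data summaries and tests, with no rule for patients unhealed at 12 months or lost earlier

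*Protocol*

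**What the plan says.** The Protocol, under Primary Endpoints, calls for weekly ulcer measurement and for recording the time to complete healing. It adds: "The point at which the ulcer has healed represents the patient reaching the primary endpoint". Under Statistical Method / Rationale, the outcome appears as "Time from intervention to healing, one part of the primary outcome", to be "described in the two randomised groups using medians, interquartile ranges and ranges (minimum to maximum), assuming the data will be non-normally distributed". The comparisons between arms are then listed: "The statistical analyses used to compare the groups will be independent samples t-tests, Mann-Whitney U tests, and chi-squared tests".

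Follow-up is finite: "Patients will be followed up via face-to-face consultations at 3, 6 and 12 months post-randomisation", and "Ulcer recurrence will not be assessed, as the follow up period is limited to 12 months". The health economic list under Secondary Endpoints includes the costs of non-healing ulcers, so ulcers that stay open are expected.

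The other primary component, the mean percentage of the ulcer healed per week, is to be calculated for each patient up to the point of healing. The statistical section calls the tests exploratory, makes summary statistics the main analysis, and gives informing a larger study as the pilot's main aim.

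The protocol mentions no censoring, no Kaplan-Meier estimate, no log-rank test, and no convention for a patient who is unhealed at 12 months or lost before then.

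**The concern.** Time to healing with a fixed end of follow-up is a censored outcome. The only feature of its distribution that the protocol anticipates is non-normality, which is a different matter. The prescribed summaries need a healing time for every patient:

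- the maximum is not observed if any ulcer in the arm stays open;
- the upper quartile is not observed if more than 25% stay open;
- the median is not observed if more than half stay open.

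An analyst following the text must choose a convention, possibly after seeing the data. The simplest choice, summarising the healing times that exist, conditions on the outcome and removes more patients from the arm that heals less.

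Objective 1 asks whether treatment shortens healing time. The medians are also a main product of a pilot meant to inform a larger trial. A difference shrunk towards zero could lead the sponsor to drop a useful treatment or to size the next trial wrongly.

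This is not a detail that the protocol leaves to an analysis plan. It names the summaries and lists the tests, and a plan using survival methods would depart from that list.

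**Working it through.** **Inputs from the Protocol.** Allocation: "This will be done to a 1:1 ratio, with 25 patients in each arm". Follow-up is 12 months, taken as 52 weeks, with weekly assessments. There is no stated figure to reproduce, because alpha, power, effect size, healing rate and loss to follow-up are not given.

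**Assumptions.** Exponential healing; healing hazard ratio 2; proportion of controls healed at 52 weeks, p, varied from 50% to 95%; loss of 0% or 10% over the year; two-sided 5% level.

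**Step 1: bias in the medians (analytic).**

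- Control hazard: λc = −ln(1 − p)/52. Treated hazard: λt = 2λc.
- True median: ln 2/λ.
- Proportion healed by week 52: P = 1 − exp(−52λ).
- Median among the healed only: −ln(1 − P/2)/λ.

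For p = 60%:

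- λc = 0.9163/52 = 0.01762 and λt = 0.03524.
- True medians are 0.6931/0.01762 = 39.3 and 0.6931/0.03524 = 19.7 weeks.
- P is 0.60 in controls and 0.84 in treated patients. Of 25 per arm, 15 and 21 heal, so a healed-only analysis drops 10 controls and 4 treated patients.
- Healed-only medians are −ln(0.70)/0.01762 = 20.2 and −ln(0.58)/0.03524 = 15.5 weeks.

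| Controls healed | True medians (weeks) | Difference | Healed-only medians | Difference |
|---|---|---|---|---|
| 60% | 39.3 vs 19.7 | 19.7 | 20.2 vs 15.5 | 4.8 |
| 80% | 22.4 vs 11.2 | 11.2 | 16.5 vs 10.6 | 5.9 |
| 90% | 15.7 vs 7.8 | 7.8 | 13.5 vs 7.7 | 5.8 |
| 95% | 12.0 vs 6.0 | 6.0 | 11.2 vs 6.0 | 5.2 |

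Differences are taken before rounding.

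**Step 2: power (simulation, 25 per arm, weekly grid, 800 runs per row).**

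| Controls healed | Loss | Mann-Whitney, healed only | Mann-Whitney, unhealed ranked worst | Log-rank |
|---|---|---|---|---|
| 50% | 0% | 0.07 | 0.43 | 0.48 |
| 60% | 0% | 0.12 | 0.47 | 0.53 |
| 80% | 0% | 0.26 | 0.55 | 0.64 |
| 90% | 0% | 0.36 | 0.54 | 0.66 |
| 95% | 0% | 0.44 | 0.52 | 0.63 |
| 60% | 10% | 0.10 | 0.47 | 0.52 |
| 80% | 10% | 0.23 | 0.52 | 0.61 |
| 90% | 10% | 0.35 | 0.50 | 0.65 |

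Cross-check of the log-rank column by Schoenfeld's formula, power = Φ(½√d · ln HR − 1.96), where d is the expected number of healings. At 60% with 10% loss, d = 14.3 + 20.2 = 34.5, so ½ × 5.874 × 0.6931 − 1.96 = 0.076 and power is 0.53. At 90%, d = 21.8 + 24.2 = 46.0 and power is 0.65. Both agree with the simulation.

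Ranking the unhealed worst costs about 4 to 13 points against the log-rank test. The last row shows 15, but a 3,000-run repeat of that scenario gave 0.50 vs 0.63, or 13 points. The Monte Carlo error of an 800-run figure is just under 2 points.

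**Step 3: a different form of effect.** If treatment changes only the proportion healed and not the speed among those who heal, healed-only power stays near 0.05 at every healing rate. The healed-only medians are then equal by construction.

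**The case against.** Four points on the other side have force.

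1. A reader might infer that unhealed patients have no place in the primary comparison. The document does not support that. It never says they are excluded; healed-only analysis is one reading of its silence. The Mann-Whitney test uses ranks, so a patient unhealed at 12 months can be placed last, and a raw median with such patients placed last is valid while more than half of an arm heals. The other primary component is calculated for each patient and can include the unhealed.

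2. A reader might infer that the method costs most of the comparison's power. That needs healed-only analysis and a control healing rate of about 80% or less. At 90% the healed-only loss is (0.66 − 0.36)/0.66 = 45% of log-rank power, and at 95% it is (0.63 − 0.44)/0.63 = 30%. The documents give no healing rate. Eligibility is limited to ulcers under 6 months old without deep venous disease, so high healing cannot be ruled out.

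3. A reader might infer an inflated false-positive rate. Healed-only analysis did not inflate it: 0.042 to 0.049 under the null with equal 10% loss. Entering the last visit as a healing time reaches about 9% only with 60% healing and a threefold imbalance in loss (30% vs 10%); with equal 10% loss it is about 5%.

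4. The tests are exploratory and no power is claimed, so power is a secondary yardstick.

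These points limit the size of the problem without removing it. Ranking the unhealed worst is not in the protocol. It also cannot properly place a patient lost at, say, week 10, whose healing may have followed soon after. The summary statistics, which are the main analysis, still need a healing time that some patients will not have.

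**Conclusion.** The point holds as a defect of a stated method. For one of its two primary components, the protocol fixes summaries and tests meant for complete data, although follow-up stops at 12 months and non-healing is foreseen, and it gives no rule for unhealed or lost patients.

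If only observed healing times are used, the bias is towards no difference. Under exponential healing and a hazard ratio of 2, the difference in medians keeps about a quarter of its true size at 60% control healing (4.8/19.7), about half at 80% (5.9/11.2) and about three quarters at 90% (5.8/7.8). The healing rates, the hazard ratio and the exponential form are all assumptions. The direction of the bias does not depend on the exact values, but its size does.

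The main harm is a misleading description passed on to the definitive trial, not a lost hypothesis test. It should be fixed, but in an exploratory pilot it does not invalidate the study.

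**What to change.** Replace the sentence on time to healing with wording such as:

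> Time from randomisation to complete healing will be described by Kaplan-Meier curves, with the median and 95% confidence interval per arm where estimable. Patients not healed will be censored at their last ulcer assessment or at 12 months, whichever is earlier. The arms will be compared by an exploratory log-rank test. The proportion healed at 12 months will be reported by arm.

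Add the log-rank test to the list of tests and state that Mann-Whitney is not used for this outcome. A Cox hazard ratio with 95% confidence interval is optional.

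Counting from randomisation also settles the time origin: the present text counts from intervention, and control patients have no intervention date.

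Censoring at loss assumes that loss is unrelated to the prospect of healing, so the number lost and the timing should be reported by arm.

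The cost is protocol wording only. The weekly assessments already supply the dates, and no extra patients or visits are needed.

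### The named group tests cannot adjust for baseline quality of life or entry ulcer area, so with 25 per arm the exploratory estimates lose precision and stay exposed to chance imbalance

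*Protocol*

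**What the plan says.** Protocol, Statistical Method / Rationale, names the group comparisons in one sentence: "The statistical analyses used to compare the groups will be independent samples t-tests, Mann-Whitney U tests, and chi-squared tests". It also sets their status: "As such, the main analysis will be summary statistics", and "Simple statistical tests will be used to compare the groups, though these analyses are exploratory and non-definitive". For the composite quality-of-life scores it adds: "The composite summary scores will be described at each point they are assessed using means, standard deviations and ranges".

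Two kinds of baseline information are available.

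- Quality of life. Under Secondary Endpoints, "The secondary measures will be measured at baseline, 3, 6 and 12 months"; these measures include EQ-5D, SF-36 and VEINES-QoL.
- Ulcer area. Inclusion criterion 1 requires "Venous ulcer of the lower limb at least 2cm²" and sets no upper limit. A baseline tracing is not stated outright, but both this criterion and a percentage healed need a starting area.

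Under Study Design, "Randomisation software will be used to allocate patients who fulfil inclusion / exclusion criteria", and "This will be done to a 1:1 ratio, with 25 patients in each arm". The section does not say whether allocation is stratified. The protocol's own answer to differing ulcer size is under Primary Endpoints, where it argues that a healing rate makes ulcers of different size comparable.

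**The concern.** Primary objective 3 asks whether scores improve, which is a question relative to where each patient started. Ulcer size bears directly on how long healing takes. The protocol has both values at entry but fixes a set of tests that cannot condition on either.

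Two things are lost. First, precision: variation in follow-up scores that the baseline score would explain stays in the standard error. Second, protection against the allocation actually obtained: with 25 per arm, one arm can easily draw smaller ulcers or better starting scores, and the unadjusted difference then includes part of that gap. This matters because the pilot is meant to inform a larger trial, whose planning needs a good estimate of the difference and of the residual SD.

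**Working it through.** The protocol gives no sample-size calculation, so there is no figure of its own to reproduce.

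**Inputs.** From the protocol: n = 25 per arm, 1:1. Assumed, because the protocol gives none: two-sided 0.05, no dropout, effects in SD units, and baseline to follow-up correlation ρ = 0.3, 0.5 or 0.7.

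**Precision for a score with a baseline value.** ANCOVA multiplies the residual variance by (1 − ρ²), so the unadjusted sample giving the same precision is 25/(1 − ρ²) per arm. The difference detectable at 80% power is (1.96 + 0.84) × √(2/25) × √(1 − ρ²). The unadjusted 95% CI half-width is t(0.975; 48 df) × √(2/25). The adjusted one is t(0.975; 47 df) × √[(2/25)(1 − ρ²)(1 + 1/46)], where the last factor is the small-sample cost of the covariate. Power is simulated, with 40,000 trials per ρ.

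| ρ | 1 − ρ² | Equivalent n per arm | Detectable difference (SD) | CI half-width (SD) | Power for 0.5 SD |
|---|---|---|---|---|---|
| unadjusted | 1 | 25 | 0.79 | 0.57 | 41% |
| 0.3 | 0.91 | 27.47 | 0.76 | 0.55 | 43% |
| 0.5 | 0.75 | 33.33 | 0.69 | 0.50 | 51% |
| 0.7 | 0.51 | 49.02 | 0.57 | 0.41 | 67% |

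**Chance imbalance.** The difference between arms in a baseline mean has SD √(2/25) = 0.283 baseline SD. So it exceeds 0.3 SD in 29% of trials and 0.5 SD in 7.7%. With no treatment effect, a 0.5 SD imbalance moves the unadjusted difference by 0.5ρ = 0.15, 0.25 or 0.35 SD. Among simulated trials with imbalance above 0.5 SD, the t-test rejects a true null in 8.7%, 15.6% and 25.7% at the three correlations, against about 5% for ANCOVA. Over all simulated trials, the t-test, Mann-Whitney test and ANCOVA each reject in about 5%.

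**Does the percentage scale deal with ulcer size?** If the percentage is of starting area, an ulcer that heals in T weeks has lost 100% over T weeks, so its mean is 100/T per week. That is the reciprocal of the other primary component, apart from the factor 100, so whatever dependence on size T has, the rate has too. Illustration, assuming the wound edge advances at a constant speed: T grows with the square root of area, so an 8 cm² ulcer takes √(8/2) = 2 times as long as a 2 cm² ulcer and shows half the weekly percentage.

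**Possible shift in healing time.** Under the same square-root assumption and an assumed SD of log area of 1.0, the difference in mean log area has SE 1.0 × 0.283. A one-SE imbalance multiplies geometric mean healing time by exp(0.5 × 0.283) = 1.152, and a 1.96-SE imbalance by exp(0.5 × 1.96 × 0.283) = 1.319. Halving the assumed SD gives exp(0.5 × 0.5 × 0.283) = 1.073 and exp(0.5 × 0.5 × 1.96 × 0.283) = 1.149.

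**The case against.** The strongest case against is that this is a descriptive pilot. The main analysis is summary statistics, the tests are declared exploratory, and no hypothesis, power or decision rule rests on them. That stands, and it limits how much the point weighs. It does not remove it: the pilot's estimates are meant to feed a larger trial, and a small sample makes chance imbalance more likely.

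Four stronger readings are tempting, and the document does not support them.

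- A reader might infer that the tests are biased or have an inflated error rate. They do not: type I error stays near 5% over all randomisations. The higher figures above apply only to the minority of trials with a large imbalance.
- A reader might infer that follow-up scores will be compared as raw means. The protocol says that scores are described at each time point and lists tests without assigning them to variables. A t-test on change from baseline would fit the text, and that choice may be in an analysis plan not seen here. It would not close the gap, though. Its variance factor is 2(1 − ρ) = 1.4, 1.0 and 0.6 at the three correlations, against 0.91, 0.75 and 0.51 for ANCOVA.
- A reader might infer that allocation is unstratified. The text neither states nor excludes stratification.
- A reader might extend the point to every comparison. Recanalization, adverse events and satisfaction have no useful baseline value.

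The protocol's own defence, the healing rate, is relevant but partial, for the reason shown in the working. It is also fair that the gain is small if ρ is only 0.3.

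**Conclusion.** The point holds as an inexpensive improvement to an exploratory analysis. The protocol itself limits the comparisons to tests that take no covariate, so an analysis plan that follows that sentence will be unadjusted. For quality of life, adjustment would be worth about 27, 33 or 49 per arm instead of 25, at assumed correlations of 0.3, 0.5 and 0.7. For healing, neither primary component is free of ulcer size, provided the percentage is of starting area. A chance imbalance in area could then pass for, or hide, a treatment difference. The size of that effect depends on an assumed growth law and spread of area, so the 15% and 32% shifts (7% and 15% at half the spread) are illustrations. Severity is modest, given the pilot aim and the exploratory label.

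**What to change.** In Statistical Method / Rationale:

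1. For EQ-5D, SF-36 and VEINES-QoL, replace the t-test with ANCOVA adjusted for the baseline score, or a mixed model over 3, 6 and 12 months with the same adjustment. Report the adjusted difference with its 95% CI.
2. Adjust the healing-rate comparison for log baseline ulcer area. The protocol names no regression model for time to healing; if one is used, adjust it in the same way.
3. State that ulcer area is traced at baseline, and that the percentage healed refers to that area if this is what is meant.
4. Keep the unadjusted summaries and the exploratory label. Leave recanalization, adverse events and satisfaction as they are.

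Stratifying the randomisation by ulcer area is optional.

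Cost: a little more analysis work and one degree of freedom per covariate (48 to 47 in a two-group linear comparison). No measurement is needed beyond those already stated or implied.
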